2.2.15.2.1 Serious Adverse Events

The number and percentage of subjects experiencing a Serious Adverse Event (SAE) will be tabulated by SOC and PT by treatment group and overall. SAEs will be counted only once for a subject within each PT and SOC.

2.2.15.2.2 Deaths

A listing of subjects who die while on study will be prepared along with the adverse event associated with the cause of death.

2.2.15.2.3 Interruptions or Discontinuations of Study Medication Due to an AE

A listing of subjects who have changes to their study medication dosing will be prepared.

2.2.15.2.4 Ocular Treatment Emergent AEs of Special Interest

As defined in protocol Section 9.3.5.5 the following Ocular AEs will be treated as TEAESIs:

- A Class II or Class III grading shift in LOCS III as defined in the Ophthalmology Manual compared to Baseline. A class II or III grading shift will be programmatically derived from the fields captured on the eCRFs in accordance with the Rosiptor Ophthalmology Manual which is the following:
 - Class II: Increase in LOCS III grade of ≥ 0.9 (NO), ≥ 1.0 (C), or ≥ 0.9 (P)
 - Class III: Increase in LOCS III grade of ≥ 1.2 (NO), ≥ 1.5 (C), or ≥ 1.5 (P)
- A reduction of 2 lines or more on the LogMAR chart in BCVA compared to Baseline
- Ocular AEs without clear etiology
- Ocular AEs considered possibly or probably related to study drug

Ocular AEs with clear etiology will be reviewed on a case by case basis to determine if they should be treated as TEAESIs. Ocular TEAESIs will be assessed by an independent, blinded adjudicator.

The number and percentage of subjects who experience a TEAESI will be tabulated by System Organ Class (SOC) and Preferred Term (PT) by treatment group and overall.

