9.3.5.5 Ophthalmic Event Reporting

All clinically significant ocular findings must be reported as AEs.

Ocular Treatment Emergent Adverse Events of Special Interest

The following Ocular AEs will be treated as treatment emergent AEs of special interest (TEAESIs)

- A Class II or Class III grading shift in LOCS III as defined in the Ophthalmology Manual compared to Baseline
- A reduction of 2 lines or more on the LogMAR chart in BCVA compared to Baseline
- Ocular AEs without clear etiology
- Ocular AEs considered possibly or probably related to study drug

Ocular AEs with clear etiology will be reviewed on a case by case basis to determine if they should be treated as TEAESIs.

Adjudication

Ocular TEAESIs will be assessed by an independent, blinded adjudicator.

Reporting of TEAESI

TEAESIs will be communicated to the Drug Safety Manager to expedite Sponsor review of events. Investigators must designate whether the event is an AE or whether it meets the criteria of an SAE ([Section 9.3.5.4.1](#)).

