2.2.15.2 Adverse Events

Counts and percentages of subjects who experienced any of the following will be presented by treatment group and overall: any AE, any drug related AE, discontinuations of study participation due to an AE, any serious adverse events (SAE), deaths, drug related SAEs, and treatment-emergent AE of special interest (TEAESI). Only those adverse events determined to be treatment emergent (TEAE) will be presented. Treatment emergent adverse events are those events with the date and time of AE onset being greater than the date and time of first dosing, and (other than TEAESIs) only those with an onset date within 28 days after the last date of dosing.

Verbatim terms on the case report forms will be linked to preferred terms and related body systems using the MedDRA Coding Dictionary version 20.0. The number and percentage of subjects who experience treatment-emergent adverse events will be tabulated by System Organ Class (SOC) and Preferred Term (PT) by treatment group and overall. Adverse events will be counted only once for a subject within each Preferred Term and System Organ Class; thus, since a subject may have more than one Preferred Term within an SOC, percentages of PT may not sum to the percentage in the SOC. If a subject reports an AE with a Preferred Term multiple times with differing severities, only the most severe is counted. If a subject reports an AE with a Preferred Term multiple times with differing relationships to study medication, only the one related to study drug is counted. Drug-related adverse events are defined as having a causality rating of being probable or possible.

All reported AEs will be tabulated as described above. For the overall AE table, number of adverse events will also be presented. In addition, a tabulation of adverse events that occur at a frequency of 2% or greater in any active treatment group at the SOC or PT level will be prepared.

AEs will also be tabulated by intensity/severity of the event (Grade 1 – mild/ Grade 2 – moderate/ Grade 3 – severe/ Grade 4 – life-threatening or disabling/ Grade 5 - death) and by Investigator's assessment of relationship to study medication (Probable, Possible or Unlikely). Adverse events judged by the Investigator to be Serious Adverse Events

(SAEs), SAEs resulting in death, AEs (regardless of seriousness) that require modification to study medication dosing (interruption or discontinuation) will also be tabulated by SOC and PT.

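### Two ocular special-interest events are exam thresholds but are tabulated only by coded AE term: a LOCS III shift may get two unreconciled counts, and a 2-line acuity loss has none of its own

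*SAP*

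**What the plan says.** SAP 2.2.15.2.4, following Protocol 9.3.5.5, lists four kinds of ocular event as TEAESIs. Two are properties of an ocular AE that has been reported: no clear cause, or a possible or probable link to study drug. The other two are exam results compared with baseline. One concerns lens grading: "A Class II or Class III grading shift in LOCS III as defined in the Ophthalmology Manual compared to Baseline". The other concerns visual acuity: "A reduction of 2 lines or more on the LogMAR chart in BCVA compared to Baseline".

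For the first, the SAP states a derivation: "A class II or III grading shift will be programmatically derived from the fields captured on the eCRFs". Cut-offs follow; Class II, for example, is "Increase in LOCS III grade of ≥ 0.9 (NO), ≥ 1.0 (C), or ≥ 0.9 (P"). For the acuity criterion it states none.

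The planned table is: "The number and percentage of subjects who experience a TEAESI will be tabulated by System Organ Class (SOC) and Preferred Term (PT"). SAP 2.2.15.2 gives one source for those terms: "Verbatim terms on the case report forms will be linked to preferred terms and related body systems using the MedDRA Coding Dictionary version 20.0".

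On entering ocular findings as AEs, Protocol 9.3.5.5 says: "All clinically significant ocular findings must be reported as AEs". Protocol 9.3.2 repeats the duty in similar terms.

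Outside the TEAESI table, SAP 2.2.15.2.6 summarises the incidence of LOCS III Class I, II and III events, singly and cumulatively. SAP 2.2.15.2.5 summarises acuity by visit and at early termination.

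**The concern.** The definition and the table use different data. A LOCS III shift or a loss of acuity lines is a value on an examination form. It acquires a verbatim term, a preferred term, a system organ class and an onset date only if someone enters an AE. The SAP finds the LOCS III shift by program, so it can identify an event for which the TEAESI table has no row. The TEAESI count in the AE overview (SAP 2.2.15.2) belongs to the same AE-based reporting, where treatment emergence is judged from an AE onset date and time.

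Ocular safety is a stated objective (Protocol 5.3), and eye disorders are of interest because of nonclinical findings that include cataracts in the 26-week rat study (Protocol 4.2.1 and 4.2.2.3). No safety monitoring committee is planned (SAP 2.2.11). A special-interest percentage that can omit subjects who meet its own numeric definition is a weak summary of that objective, and a reader of the report could not tell that it had done so.

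**Working it through.** No expected TEAESI rate appears in the documents, so there is no figure of the plan to reproduce. The check is a reading of the sections side by side, then simple arithmetic on what one subject is worth.

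**Step 1. Trace each criterion to a count.**

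| TEAESI criterion | Derived from exam data? | Has SOC and PT without AE entry? | Counted elsewhere? |
|---|---|---|---|
| LOCS III Class II/III shift | Yes, with cut-offs (SAP 2.2.15.2.4) | No | Yes, class incidence (SAP 2.2.15.2.6) |
| BCVA loss of 2 or more lines | No rule given | No | No; visit summaries (SAP 2.2.15.2.5) and subject listings (Protocol 10.1, SAP 2.1) only |
| Ocular AE without clear cause | Not needed | Already an AE record | General AE tables |
| Ocular AE possibly or probably related | Not needed | Already an AE record | General AE tables |

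The last two rows raise no difficulty. The first two depend on AE entry.

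**Step 2. Is AE entry assured?** Two readings are open.

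- *Entry is limited.* The explicit duty in Protocol 9.3.2 and 9.3.5.5 turns on clinical significance, which is the investigator's judgement and not the numeric threshold.
- *Entry is complete.* Both documents introduce the four items as ocular AEs. Protocol 9.3.5.5 has the investigator designate each TEAESI as an AE or an SAE, and Protocol 9.3.5.6 requires all AEs on the eCRF. On this reading every crossing gets a term.

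Neither document settles which applies. The SAP has no step that creates or queries an AE for a derived shift, gives it a term, or compares the two sources.

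**Step 3. Consequence if a crossing is not entered.**

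- LOCS III shift: no row in the TEAESI table, but still counted in SAP 2.2.15.2.6. The report can then show two different numbers of Class II/III subjects with no rule to reconcile them.
- Acuity loss: no row in the TEAESI table and no count elsewhere. A mean or median by visit does not show how many men lost two lines. The SAP also does not give the LogMAR change that equals two lines, which eye is used, or which visits apply.

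**Step 4. What one subject is worth.** Planned size is 45 per arm with 10% discontinuation (SAP 2.2.1): 45 / (1 − 0.10) = 50 per arm, which agrees with about 100 randomised 1:1 (SAP 2.2.4.1). One uncounted subject is 1 / 50 = 2 percentage points of that arm's TEAESI rate.

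**Step 5. Illustration on assumed rates.** Let *p* be the share of an arm that crosses a threshold and *r* the share of those entered as AEs. Neither is in the documents. The table would show 50 × *p* × *r* of the 50 × *p* true crossers:

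| Assumed *p* | True crossers per arm | Shown at *r* = 25% | Shown at *r* = 75% |
|---|---|---|---|
| 4% | 2 | 0.5 | 1.5 |
| 10% | 5 | 1.25 | 3.75 |
| 20% | 10 | 2.5 | 7.5 |

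At *r* = 100% nothing is lost. A man with an unentered crossing who also has another ocular TEAESI recorded as an AE still counts in the total, so the effect on the total may be smaller than shown.

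**The case against.** The strongest reply is that the documents already treat both thresholds as AEs: the list is headed that way, and the AE-or-SAE designation leaves no third option. If sites follow that, every crossing is coded and the SOC/PT table is complete. The Ophthalmology Manual, which is not available here, may say so outright. This stands in part. It makes the loss conditional, not certain. It does not remove the point, because the explicit entry duty rests on clinical significance and the SAP never checks the examination data against the AE records.

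It is also fair to say that LOCS III is largely covered. SAP 2.2.15.2.6 counts class events regardless of AE entry, and Appendix C adds a longitudinal model. That stands, and it confines the LOCS III problem to two counts that may disagree.

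A reader might infer more than the documents support:

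- *That the main ocular safety result rests on investigator judgement.* The ocular objective and endpoints name LOCS III, BCVA, IOP, corneal staining and slit lamp findings. Nothing makes the TEAESI percentage the lead result.
- *That unentered crossings would not reach the adjudicator.* Both documents say ocular TEAESIs are assessed by an independent blinded adjudicator, and neither limits referral to entered AEs. The route is unstated, not shown to be closed.
- *That the eye-disorder rates of 7% and 10% in earlier Phase 2 trials show the size of the loss.* Those are rates for a whole MedDRA organ class in other diseases, not rates of LOCS III shifts or 2-line losses.
- *That the comparison between arms is biased.* Investigators are blinded, and nothing in the documents suggests that entry would differ by arm.

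**Conclusion.** The point holds in a conditional form. Because TEAESIs are tabulated by SOC and PT, the table can undercount subjects who meet the SAP's own numeric definition if a crossing is not entered as an AE, and the documents do not settle whether every crossing must be. For LOCS III the result would be two unreconciled counts. For a 2-line acuity loss the gap does not depend on AE practice in one respect: no derivation or separate count exists anywhere, only visit summaries and listings. That is the firmer half.

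The number of subjects affected cannot be known from the documents. At about 50 men per arm each uncounted subject is 2 percentage points; the ranges in the working are illustrations on assumed rates. The data themselves are collected and listed, so nothing is lost beyond recovery. The change is worth making before unblinding because it affects a stated safety result and uses data already recorded.

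**What to change.** 1. Derive BCVA loss of two or more lines from the recorded LogMAR values by program, as the SAP already does for the LOCS III shift. State the LogMAR change that counts as two lines. Apply it per eye, count the subject once by the worse eye, and use all post-baseline visits including early termination and 6 months. The 6-month exam belongs because SAP 2.2.15.2 exempts TEAESIs from the 28-day cut-off.
2. Tabulate TEAESI subjects by criterion (LOCS III shift, acuity loss, AE without clear cause, related AE) and in total, each subject once in the total. Keep the SOC/PT table for entered AEs.
3. List derived events with no matching AE. Reconcile those found through Week 16 before the interim lock and unblinding in SAP 2.2.12.
4. Pass all such events to the existing blinded adjudicator. The 6-month exams are reported after the study is unblinded, so the SAP should say that the adjudicator stays blinded for them.

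The cost is one extra derivation, one reconciliation listing and the time to work through it. No visit or procedure is added and the efficacy analysis is untouched. The TEAESI count may rise slightly.

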2.2.15.2.5 Ophthalmic Safety

Ophthalmic safety will be summarized by treatment groups and overall at Baseline, Week 12, Week 16 and 6 months post last dose: assessment of lenticular opacification using LOCS III grading system, best corrected visual acuity (BCVA) using the LogMar chart (i.e., after manifest refraction), and Intraocular Pressure (IOP) before and after dilation. Summaries will also be provided at early termination, although such summaries are acknowledged to not be a representative sample of the distribution. Number and percentage of subjects detected with corneal stain and abnormal slit lamp examination results will be presented at Baseline, Week 12 and 6 months post last dose.

2.2.15.2.6 Analysis of LOCS III

Change from baseline in LOCS III score to each scheduled visit will be summarized by treatment group. Incidence of class events (Class I, Class II and Class III) will be summarized. Incidence of cumulative events (at least a Class I event, at least a Class II event and a Class III event) will be summarized and p-values will be provided for descriptive purposes, using a chi-square test. The definition of class I, II and III events are described in the Rosiptor Ophthalmology Manual.

The LOCS III grading system values will also be analyzed by means of a longitudinal MMRM model which accounts for the between-eye correlation. The details of this MMRM is provided in Appendix C – LOC III Grading System MMRM Analysis.

2.2.15.3 Laboratory Data

Shift tables will be presented showing the shift in (Normal/Low/High) from baseline to Week 12, off treatment follow-up and early termination visit by treatment group.

2.2.15.4 Vital Signs, 12-Lead ECG, physical examination and Other Observations Related to Safety

Vital signs include blood pressure and heart rate. Actual values and change from baseline will be tabulated by treatment group at baseline and each post-baseline.

Shift tables will be provided for ECG data (Normal/Abnormal) from Screening Visit to Week 12, off treatment follow-up and early termination visit by treatment group.

Physical Examination Findings will be presented in the listings but not tabulated.

2.2.15.5 Concomitant Medications

Concomitant Medications will be coded per the WHO Drug Dictionary B3 Global (version effective March 2017). Concomitant Medications will be tabulated by treatment group, Drug Class (pharmacological level, ATC3) and Drug Name (chemical substance level, ATC5). These data will be provided in subject data listings along with the verbatim drug term and usage details.

Use of concomitant analgesic medication will be summarized with the percentage (%) of subjects taking each class of medication using subjects who took any such medication on at least 1 of the 7 days prior to the Baseline, Week 6 or Week 12 Visit).

References

- O'Kelly, M., & Ratitch, B. (2014). *Clinical Trials with Missing Data: a Guide for Practitioners*. Wiley.
- Alut, K. *Multiple Imputation for Ordinal Variables: A Comparison of SUDAAN PROC IMPUTE and SAS® PROC MI*, SESUG 2012, Paper SD-12, 2012.

3 Document Version Control

Revision History:

| REVISION | RELEASE DATE | AUTHOR | SUMMARY OF CHANGES |
|----------|---------------|---------------------|--------------------|
| A | June 25, 2018 | [name] | Initial Release |
| | | | |
| | | | |
| | | | |

Appendix A - Programming Specifications for Tables and Listings

The following specifications will be used in the production of tables and listings.

1. Page Setup

Unless otherwise noted, tables and listings will use landscape orientation. Margins will be at least 1.5 inches on the bound side and at least 1 inch on the other three sides.

The following header information should be included:

- Upper left: Sponsor name and protocol number
- Center: CONFIDENTIAL
- Upper right: Page number shown as Page n of N. Page numbers should be sequential within a table or listing.

The footer should include:

- The name of the SAS program used to generate the output along with the run date/time and the words “by CTDS”.
- For tables, the corresponding listing number(s).
- For figures, the corresponding table number.

2. Footnotes

Unless otherwise specified, footnotes should appear on all pages within the table.

3. Font

Font will be 8-point Arial, or smaller if needed for space constraints. If possible, small tables should appear on one page. If tables continue on to multiple pages, there should be a page break after an assessment so that all the statistics for an assessment appear on the same page.

4. Tables

Table titles should reflect the content of the table. Under the main title, in parentheses, the name of the analysis population being summarized should appear.

4.1 Summary Statistics - Continuous Data

Unless otherwise noted, the mean and median and confidence interval (CI) of a set of values should be printed out to one decimal place more than the original value. The standard deviation should be printed out to 2 decimal places more than the original value. The number of subjects on whom the parameter is assessed should appear. Minimum and maximum should be consistent with the original value. P-values will be

expressed as 4 decimal places. Any p-values that get calculated as 0.00005 or less should be expressed as $P < 0.0001$.

4.2 Summary Statistics - Categorical Data

Numbers of subjects are reported as whole numbers. Null counts are represented as 0. Table percentages should be reported to one decimal. Null percentages will be suppressed (i.e., just showing the null count of 0).

For all categories, the total number of subjects with data will be presented as N and the number of subjects with non-missing data will be used as the denominator for the calculation of the percentages, unless otherwise stated in a footnote.

5. Subjects Included in Listings

In general, subject data listings should include all subjects who signed the informed consent. If a listing includes a subset of subjects who meet a certain condition (e.g., subjects with SAEs) then this should be clear from the title of the listing. If there are no subjects who meet the condition (e.g. no subjects with SAEs) for either the tables or the listings, then a page marker should appear stating that no subjects met the criteria.

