2.2.5.1 Intent to Treat (ITT) Population

The ITT Population will include all randomized subjects. In the event of study drug administration error, analyses on the ITT Population will be performed according to the treatment which the subject was randomized to receive.

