2.2.10 Methods for Handling Missing Data

2.2.10.1 Missing Daily Data in the Weekly Scores

For endpoints which are the average of a daily score across a week (e.g., maximum daily pain and average daily pain), if the subject has 4 or more non-missing values in that week, the weekly mean score will be calculated as the average of the non-missing values, otherwise the weekly mean score will be set to missing for that week.

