2.2.13 Efficacy Analyses

The primary efficacy analysis population will be the ITT Population.

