The MMRM model to assess time course will have treatment as a factor, the corresponding baseline value as a covariate, a linear term for time (in weeks), and a time×treatment interaction effect term. The model will allow for a subject random intercept and slope over time with an unstructured correlation matrix. Sample SAS code for the time course MMRM is provided in Appendix B – Sample MMRM Code.

For response to treatment as measured by the GRA and PGI-C at Week 12 (Visit 4), the frequency distribution of each response scale will be presented by treatment group and assessed using a chi-square row mean score difference test.

- The GRA response is a 7-point Likert scale (range: -3 to 3) with a score of -3 indicating “Markedly Worse”, a score of 0 indicating “No Change”, and a score of 3 indicating “Markedly Improved” to the question: *As compared to when you started the study drug, how would you rate your Chronic Prostatitis / Chronic Pelvic Pain Syndrome symptoms now?*
- The PGI-C response is a 7-point Likert scale (range: 1 to 7) with a score of 1 indicating “Very much improved”, a score of 4 indicating “No change”, and a score of 7 indicating “Very much worse” to the item: *Choose the response that best describes the overall change your pelvic pain since you started the study.*
- The PGI-S response is a 5-point ordinal scale with a score of 1 being “None” and a score of 5 being “Very Severe” to the item: *Choose the response that best described the severity of your chronic prostatitis / chronic pelvic pain symptoms over the past week.*

For response to treatment as measured by the PGI-S at Week 12 (Visit 4), the frequency distribution of each response scale will be presented by treatment group and the change from baseline will be assessed by an ANCOVA model with treatment as a factor and baseline PGI-S as a covariate.

For the following two dichotomous secondary efficacy endpoints the rates for each treatment group and difference between the treatment groups will be presented with corresponding 95% CIs. A CMH test will be used to test for differences in rates between the treatment groups controlling for baseline pelvic pain. The baseline pelvic pain will be stratified into 2 categories (4-7 and >7):

- (1) Treatment response as defined by meeting either of the following:

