 - Decrease in maximum daily pelvic pain (mean) from Baseline to Week 12 using a standardized 11-point NRS with no change in the amount or strength of concomitant analgesic medications (as defined in Section 2.2.14).
 - Decrease in maximum daily pelvic pain from Baseline to Week 12 using a standardized 11-point NRS with a decrease in the amount or strength of concomitant analgesic medications (as defined in Section 2.2.14).
- (2) A $\geq 30\%$ and $\geq 50\%$ improvement (decrease) in maximum daily pelvic pain (mean) (using the 11-point NRS recorded by eDiary and the NIH-CPSI pain subscale), at Weeks 6 (Visit 3) and 12 (Visit 4).

For the Discontinuation of study medication due to treatment failure endpoint, only summary statistics will be provided for the percent meeting treatment failure criteria and the time to event (no inferential analyses will be performed). Time to discontinuation of study medication due to treatment failure will be summarized and presented graphically using Kaplan-Meier methods (i.e., SAS PROC LIFETEST stratifying on treatment group).

The frequency distribution of the 5-category IIEF-EF score will be presented by treatment group for Week 12 as well as a shift table from Baseline. The 5 categories are no erectile dysfunction (score: 26-30), mild erectile dysfunction (score: 22-25), mild to moderate erectile dysfunction (score: 17-21), moderate erectile dysfunction (score: 11-16) and severe erectile dysfunction (score: 1-10). Responses to all items must be completed to calculate an IIEF-EF score. Any response with missing values will be excluded from the analyses. Treatment group difference

with corresponding 95% CIs in the 5-category IIEF-EF will be assessed by a Cochran-Mantel-Haenszel (CMH) test using row mean scores controlling for Baseline IIEF-EF score.

Data from both treatment arms will be used to calculate a meaningful change threshold (MCT), which reports a change in the primary endpoint (change in maximum daily pelvic pain) by anchoring to other outcomes (including PGI-S and/or PGI-C) to determine a change in maximum pelvic pain that provides a meaningful benefit to patients. The determination of the MCT will be made outside of the methods documented in this SAP prior to database lock. Once the MCT is determined, the proportion of subjects who have an improvement of at least the MCT will be summarized by treatment group and compared using a chi-square test as an exploratory analysis.

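### Responder rates default to subjects with data at the visit although efficacy is declared ITT, which biases the difference if one arm loses more failures than the other

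*SAP*

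**What the plan says.** The denominator rule is a general table convention. SAP Appendix A, 4.2 states that "the number of subjects with non-missing data will be used as the denominator for the calculation of the percentages", with the exception "unless otherwise stated in a footnote". The SAP specifies no such footnote for the responder tables.

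For treatment response and for ≥30% and ≥50% improvement, SAP 2.2.13.3 says that "the rates for each treatment group and difference between the treatment groups will be presented with corresponding 95% CIs". It adds: "A CMH test will be used to test for differences in rates between the treatment groups controlling for baseline pelvic pain". It does not say how to classify a subject whose status at Week 6 or Week 12 cannot be determined.

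The nearby rules do not fill the gap:

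- SAP 2.2.10.1 needs at least four daily values for a weekly diary mean; "otherwise the weekly mean score will be set to missing for that week". SAP 2.2.13.1 applies the same minimum to the seven days before the clinic visit.
- SAP 2.2.10.2 and 2.2.13.2 set out multiple imputation under MAR and under a placebo-based MNAR model, for the primary efficacy analysis only.
- SAP 2.1 has Early Termination assessments summarized descriptively and does not carry them into Week 12 efficacy.

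On the population, SAP 2.2.13 says "The primary efficacy analysis population will be the ITT Population" and SAP 2.2.5.1 says "The ITT Population will include all randomized subjects".

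**The concern.** A responder percentage reported for the ITT population will usually be read as a fraction of everyone randomized. Under the default rule it is a fraction of those with a usable value at that visit. A man without one leaves both numerator and denominator.

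Some of this loss may be linked to poor outcome. Protocol 7.3 lists intolerability, disease progression and other available treatments among the reasons for stopping the drug. Staying in follow-up afterwards is encouraged but cannot be assured. If one arm loses more failures than the other, its observed-case rate rises further, and the difference and its CI shift in its favour.

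The responder analysis also handles missing data less fully than the analysis it is meant to help interpret. The MMRM keeps the Week 6 value of a man who has no Week 12 value, and it has two imputation-based sensitivity analyses. The Week 12 responder rate uses nothing from that man and has no missing-data sensitivity analysis.

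**Working it through.** **The plan's own figures.** The documents give no responder rate, no responder power and no missing-data rate by arm. They do give the primary sample size (Protocol 10.2, SAP 2.2.1): difference 1.2, SD 2.0, two-sided 5%, 45 per arm, 10% discontinuation of study drug, about 100 randomized. The noncentral t distribution gives 80.4% power at 45 per arm and 79.5% at 44, and 90/(1 − 0.10) = 100. These reproduce and are not in dispute. They supply only the scale used below: 50 per arm, with 10 missing of 100 as an upper reading of the 10% rate.

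**Assumptions (not from the plan).** True response is equal in the two arms, and every missing subject is a failure.

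**Formula.** With r responders and m missing, the observed-case rate is r/(50 − m) and the full-denominator rate is r/50. With r = 20 in each arm, the full denominator gives 40.0% in both arms, a difference of 0, whatever the split. The default gives:

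| Missing, AQX-1125 / placebo | AQX-1125 | Placebo | Difference |
|---|---|---|---|
| 5 / 5 | 20/45 = 44.4% | 20/45 = 44.4% | 0 |
| 8 / 2 | 20/42 = 47.6% | 20/48 = 41.7% | +6.0 points |
| 10 / 0 | 20/40 = 50.0% | 20/50 = 40.0% | +10.0 points |
| 3 / 7 | 20/47 = 42.6% | 20/43 = 46.5% | −4.0 points |

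For response rates from 30% to 50% (r = 15 to 25), the false difference is 4.5 to 7.4 points at 8/2 and 7.5 to 12.5 points at 10/0.

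**Nominal significance with no true effect.** This was simulated with 200,000 runs per setting, an unstratified two-sample test rather than the planned stratified CMH, and missing counts that equal the stated splits on average. For response rates of 30% to 50%, two-sided P<0.05 occurs in about 5% of trials at 5/5, 7% to 11% at 8/2 and 12% to 22% at 10/0. With the full denominator it is about 5% to 6%.

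**The opposite case.** Suppose missingness is unrelated to response and the true rates are 50% and 40%. Observed-case rates are then unbiased, with a difference of 10 points. Counting missing as non-response gives:

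- 20% and 10% missing: 0.50 × 0.80 − 0.40 × 0.90 = 0.04, or 4 points
- 15% and 10% missing: 0.50 × 0.85 − 0.40 × 0.90 = 0.065, or 6.5 points
- 10% and 10% missing: 0.50 × 0.90 − 0.40 × 0.90 = 0.09, or 9 points

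These three figures show how far the two methods can differ. They do not measure bias in the default.

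**The case against.** The strongest reply is that stopping the drug is not the same as missing data. Protocol 7.3 and 7.4 separate the two, and Protocol 6.1 asks men who stop treatment to continue visits, stressing pelvic pain data. The diary runs to Week 16. A man who stops for lack of effect but has four diary scores before the visit stays in and can count as a failure. This stands. A reader might infer a completer analysis, but the documents do not support that: the plan calls completers those who finish 12 weeks of treatment, whereas the default depends only on data at the visit.

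A reader might also infer bias toward whichever arm has more dropouts. That does not follow. Missing subjects must also respond less often than observed ones, and the bias can favour either arm. Nothing in the plan predicts a large imbalance. In the earlier Phase 2 trials (Protocol Table 2), TEAEs leading to discontinuation were 6% on AQX-1125 and 5% on placebo, although that covers only one reason for stopping. The uneven splits above are illustrations, not forecasts.

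Three further points stand:

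- The table rule governs percentages. That the CMH test and CIs also drop missing subjects is the natural reading, not a stated rule.
- Loss will be partly visible. The same rule shows the number with data as N, SAP 2.2.7 reports disposition by arm, and SAP 2.2.13.3 summarizes discontinuation for treatment failure. None of these corrects the responder rates.
- Responder P values are descriptive, and the primary analysis has its own missing-data sensitivity analyses.

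The reply does not supply a rule. Without one, a table-formatting convention sets the estimate.

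**Conclusion.** The point holds in limited form. By default, responder results are observed-case by visit under an ITT label, with no missing-data sensitivity analysis.

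The size depends on facts that the plan does not give. With equal true rates and balanced loss of failures, both rates rise and no false difference appears. With 10 missing failures in total and 40% true response in each arm, an 8 versus 2 split produces a false 6 points. The 10-point figure needs all 10 in one arm and is an extreme. If missingness is unrelated to response, there is no bias to correct.

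The primary MMRM is untouched. The gap merits a change before unblinding because responder rates are meant to help interpret the primary result and the change is small.

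**What to change.** In SAP 2.2.13.3, state that responder rates, their CIs and the CMH test use all ITT subjects, with missing responder status at that visit counted as non-response. Apply this also to the composite response when status cannot be determined from the diary pain and analgesic data together, since SAP 2.2.14 gives no rule for missing analgesic entries. Add the matching footnote to the tables so that the Appendix A default does not override it.

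Report two further versions:

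- Observed-case rates as supplementary, for all responder endpoints.
- For the diary ≥30% and ≥50% endpoints, rates derived from the multiply imputed datasets already planned, as sensitivity. The planned imputation does not cover the NIH-CPSI pain subscale or analgesic use.

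Before those datasets are reused, clarify the scale of the imputation limits. SAP 2.2.10.2 imputes change scores but sets limits of 0 to 10 for pain values. A lower limit of 0 on a change score would rule out any imputed improvement.

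The cost is a few SAP sentences and modest programming. Reported rates will be lower, and a man still in the study with too few diary days will count as a non-responder. The imputation-based version addresses that for the diary endpoints.
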